1 BACKGROUND INFORMATION AND RATIONALE

A.1. Impact of preterm delivery (PTD) and low birthweight (LBW) on patients and society

PTD, defined as birth before 37 completed weeks of gestation, together with LBW, is the **leading cause** of perinatal mortality and morbidity. It accounts for about 30% of early neonatal deaths worldwide^{1,2}. It is also the leading cause of congenital neurological disabilities including cerebral palsy, blindness and deafness, and learning disability in the U.S. and most developed countries^{3,4}. In addition, PTD is the major cause of admission to the neonatal intensive care unit (NICU) and a significant contributor to medical expenditure for infants. In the U.S. alone, the costs associated with PTD amount to more than **\$26 billion** each year, and continue to rise⁵⁻⁷. Such impact on infant health and on staggering medical and economic costs makes PTD one of the most serious challenges for clinicians and biomedical researchers today and it has become a global crisis. Leading international and national organizations including the World Health Organization (WHO), Institute of Medicine (IOM), and March of Dimes all have listed prevention and reduction of PTD as a top research priority⁸⁻¹⁰. One of the key reasons why PTD is a top research concern is that, despite decades of effort, there is a lack of progress in identifying modifiable risk factors, and thereby a lack of strategies to develop effective interventions to reduce PTD¹⁰. Consequently, the incidence of PTD has not been reduced. Currently, in the U.S., about 12% of all births (about **half a million births**) are the result of PTD each year, and many are admitted to NICUs. Such impact on patients and the staggering costs also make PTD (together with LBW) one of the top research priorities of PCORI and AHRQ¹¹.

A.2. Genital herpes infection in relation to adverse pregnancy outcomes

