Treating pregnant women is unique in that it impacts *both* the mother and her developing fetus. CDC has highlighted a new initiative called "**Treating for Two**" and advocated research into medication use during pregnancy to take into account the effectiveness and risk-benefit profiles for both pregnant women and the developing fetus (<http://www.cdc.gov/pregnancy/meds/treatingfortwo/>)⁴². Currently, symptomatic genital herpes infection in pregnancy, usually considered more severe than asymptomatic genital herpes, is mostly treated with anti-herpes medications, such as acyclovir, that are effective in suppressing viral shedding and symptoms²³. Acyclovir is also recommended for treating genital herpes after 36 weeks of gestation to prevent vertical transmission of maternal herpes infection to the newborn^{23,24}. On the other hand, asymptomatic genital herpes before 36 weeks of gestation is often left untreated because of a lack of recognized benefits for fetal outcomes (e.g., reducing PTD and LBW). Thus, many women with mild or asymptomatic genital herpes are left untreated, and, consequently, at increased risk of PTD and LBW^{17,19-22}. Untreated genital herpes infection was associated with more than twice the risk of PTD and more than 40% of increased risk of LBW, compared to controls as described above. More importantly, if treated with acyclovir, women with genital herpes had a more than 50% reduced risk of PTD (OR=**0.49**, 95%CI=0.36-0.68), and 40% reduced risk of LBW (OR=**0.60**, 95%CI=0.37-0.98) than women who were not treated (Tables 2). Our preliminary results showed that the currently recommended treatment of herpes infection with acyclovir, if expanded to treat pregnant women with genital herpes before the 3rd trimester, could largely mitigate the risk of PTD and LBW associated with genital herpes infection. This treatment effectiveness was also consistent across subtypes of PTDs.

A lack of consistency in treating genital herpes infection in pregnant women is largely due to the knowledge gap regarding (1) increased risk of PTD and LBW associated with untreated

genital herpes infection in pregnant women, and (2) evidence of treatment effectiveness in reducing PTD and LBW, in addition to preventing mother-newborn vertical transmission of herpes infection^{17,19-21,35}.

A.4. Existing knowledge gaps

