3.3.3 Populations

Stage I population

All KPNC women aged 18 years (the minimum age required by our KPNC IRB) or older who are pregnant beyond 20 weeks of gestation during the recruitment period will be included to form the Stage I population, estimated at 90,000. These women will be assigned to one of the four cohorts based on diagnosis and treatment of genital herpes infection. Identification of genital herpes will be based on information from multiple databases captured by KPNC EMR including clinical diagnosis, laboratory testing and viral culture, prenatal screening inventory, and medical history. Treatment will be determined through prescription and dispensing of anti-herpes medications from the pharmacy data. Based on the combination of infection and treatment as well as the specific aims, we expect to establish four cohort groups. information currently available information, we expect a total of 2,100 women with genital herpes receiving treatment before the 3rd trimester (Cohort A), 2,100 women with genital herpes receiving treatment after the 3rd trimester (Cohort B), 6,600 women with untreated genital herpes (Cohort C), and 79,200 controls with neither genital herpes nor treatment (Cohort D), as shown in Figure 1. A small adjustment may need to be made at the end of pregnancy, if the status of the infection and/or treatment has changed since the initial assignment to each comparator (e.g., from untreated to treated). Through the KPNC EMR, we will have information on genital herpes infection and treatment during pregnancy (the exposure variables), and PTD and LBW (the outcome variables) (Table 4) as well as many potential confounders (Table 5) for all 90,000 pregnant women. This large Stage I population will provide a large powerful study population to examine comparative effectiveness of genital herpes treatment in reducing adverse pregnancy outcomes, addressing the questions listed in the specific aims.

Stage II samples

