Point and interval estimates of the relative hazards of PTD associated with first treatment during pregnancy before and first treatment during the 3rd trimester will be obtained (Cohort A vs. B) by extending the Aim 1 regression model to capture treatment timing. Parameter estimation, the approach to inclusion of potential confounders, modeling of continuous covariates, and model diagnostics are as described above for Aim 1 analyses. Treatment will be handled as a time-varying covariate for proper classification of exposure status in each risk set for the Cox regression (three levels: no treatment, first treatment < 3rd trimester, treatment in 3rd trimester). Significance of the difference between strength of association across the two treatment timing categories will be assessed via a Wald test.

Aim 3. Do other treatment metrics, including treatment duration, dosage, and compliance, impact treatment effectiveness in reducing PTD and LBW risk?

Metrics of treatment exposure of interest will be treated as time-dependent covariates in Cox regression analyses to account for changes in exposure status during follow-up, including cumulative duration (categorized as no use, 1-5 days, 6-10 days, 11-30 days, and > 30 days) based on clinical prescription patterns, and cumulative dose (categorized as no use, 1-4,800mg, 4,801-12,000mg, and >12,000 mg) also based on current clinical prescription patterns. In addition to examining these metrics in relation to pregnancy outcomes during the entire pregnancy, we will also assess trimester-specific measures of treatment duration and dose.

Aim 4. Does treatment effectiveness vary depending on the type (or severity) of underlying genital herpes infection? (e.g. treating symptomatic genital herpes infection vs. treating latent/asymptomatic genital herpes)

Analyses will examine potential heterogeneity in association between treatment and PTD across infection characteristics via the inclusion of appropriate cross-product terms and a likelihood ratio test, and point and interval estimates of association at each level of the effect modifier will be obtained via appropriate transformed linear combinations of regression parameter estimates.

Aim 5. Does genital herpes infection in pregnancy, if untreated, increase the risk of PTD and LBW, compared to no genital herpes infection? (untreated vs. controls without genital herpes) .

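### The PTD Cox models switch treatment on at first treatment with no lag, so any third-trimester starts prompted by an expected early delivery would tilt the Aim 2 PTD contrast towards early treatment

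*Combined protocol and SAP*

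**What the plan says.** Under Aim 2, section 4.2 states: "Treatment will be handled as a time-varying covariate for proper classification of exposure status in each risk set for the Cox regression". The covariate has "three levels: no treatment, first treatment < 3rd trimester, treatment in 3rd trimester", and the two timing levels are compared by a Wald test. The model is described as an extension of the Aim 1 model. Aim 3 also treats duration and dose as time-dependent. No lag, induction period or latency window is given for Aims 1 to 3. The plan is silent here; it does not state a zero-lag rule.

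On the source of exposure, section 3.3.3 says: "Treatment will be determined through prescription and dispensing of anti-herpes medications from the pharmacy data". No rule uses the reason for starting.

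On why treatment is given late, section A.3 says: "Acyclovir is also recommended for treating genital herpes after 36 weeks of gestation to prevent vertical transmission of maternal herpes infection to the newborn". It adds that "asymptomatic genital herpes before 36 weeks of gestation is often left untreated because of a lack of recognized benefits for fetal outcomes". Section A.1 fixes the end of the risk period: "PTD, defined as birth before 37 completed weeks of gestation".

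Section 3.4 takes late starters to be comparable with early starters apart from timing. Low birthweight (LBW) is analysed by logistic regression in all aims.

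**The concern.** Late treatment is described as protection for the newborn at birth, and treatment of asymptomatic infection before 36 weeks as uncommon. Third-trimester starts before 36 weeks are therefore selective. Some may be made because an early delivery is already in prospect (preterm labour, ruptured membranes, planned early delivery). Followed as written, the model then counts a birth a day or two after first dispensing as a late-treated PTD, although the drug had no time to prevent it. Time-varying coding removes immortal time but not this reverse causation.

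A small number of such women would matter, because late-treated time at risk is short. A woman who starts at 36 weeks contributes at most 7 treated days before 37 weeks. The effect would be to make late treatment look harmful and early treatment look better than late, which is the direction section A.4 already expects. The pooled Aim 1 contrast would be pulled towards no benefit. The short-duration categories in Aim 3 (1-5 and 6-10 days) would collect the same births.

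**Working it through.** **1. The plan's own Aim 2 figure.** Inputs from section 4.5: effective size 1,200 per cohort (2,400 for A vs B), two-sided alpha .05, power .80. Detectable HR = exp(-(1.960 + 0.842) / sqrt(events / 4)).

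- 8% PTD: 2,400 x 0.08 = 192 events; exp(-2.802 / sqrt(48)) = 0.667 (Table 6: .66).
- 11% PTD: 2,400 x 0.11 = 264 events; exp(-2.802 / sqrt(66)) = 0.708 (Table 6: .71).

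Table 6 reproduces. The issue is bias, not sample size.

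**2. Null simulation of the planned model.** From section 3.3.3: 2,100 (A) + 2,100 (B) + 6,600 (C) = 10,800 infected women. From section 4.5: 8% PTD. The remaining inputs are assumptions, not document figures:

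- no true drug effect, and a third trimester that starts at 28 weeks;
- PTD timing of 6/12/14/28/40% over 20-28, 28-32, 32-34, 34-36 and 36-37 weeks;
- 50% or 80% of routine late starts at or after 36 weeks;
- reactive starts 0-7 days before delivery;
- 0, 1 or 3 false alarms (women who start for the same reason but deliver at term) per reactive start.

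The fitted model is the three-level time-varying Cox model with daily risk sets.

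| Reactive share of not-yet-treated women with third-trimester PTD | Women of 10,800 | Late vs untreated, lag 0 | A vs B, lag 0 | A vs B, lag 7 days | A vs B, lag 14 days |
|---|---|---|---|---|---|
| none | 0 | 1.01 | 1.00 | about 1.00 | about 1.00 |
| 5% | about 29 | 1.33-1.60 | 0.66-0.79 | 0.87-0.98 | 0.99-1.10 |
| 10% | 56-59 | 1.67-2.30 | 0.48-0.66 | 0.77-0.97 | 0.99-1.21 |

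**3. Hand check.** Cohort A has about 2,100 x 0.08 = 168 PTDs. With no reactive starts, late-treated PTD events number only 92 (half of late starts at or after 36 weeks) or 62 (80%), because a late starter must still be pregnant when she starts. Adding the reactive births alone multiplies A vs B by about 92 / (92 + 28) = 0.77, or 62 / (62 + 29) = 0.68. The simulation agrees.

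**4. Other assumptions.** A separately built simulation with about 30 reactive starts gave 0.63-0.78; another, at 5%, gave 0.58-0.81. With 9% PTD and starts 1-3 days before birth, a 2% share (about 14 women) gave 0.79-0.81.

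**5. Does a lag cure it?** Not reliably.

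- If reactive starts fall 3-14 days before birth, A vs B at a 7-day lag is still 0.59-0.78.
- With three false alarms per reactive start, a 14-day lag overshoots to 1.03-1.21 at 5-10%.
- With 80% of late starts at 36 weeks and no reactive starts, a 7-day lag cuts late-treated PTD events from about 61 to 24.
- Leaving a woman in her previous state when her start follows a recorded encounter for impending early delivery gives 0.94-1.02, provided the encounters are captured.

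**The case against.** The strongest objection is to the premise. Section A.3 gives a gestational-age threshold for late treatment. It does not say that an individual woman's start follows her expected delivery date, and it names none of the triggers above. No frequency can be taken from the documents, and with none the planned coding is unbiased. This stands: the bias is conditional, and its size rests on an assumed share.

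The plan also has partial safeguards:

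- Section 3.1 allows time-dependent covariates.
- Section 4.2 tests exposure by gestational age.
- Section 4.4 uses prescribing preference as an instrument against unmeasured confounding.
- Table 5 lists confounders but is not in the text available here, so it cannot be said that obstetric complications are left out.

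Nothing in the available text is aimed at imminent delivery as the reason for starting. The propensity score in section 4.3 models treatment vs none, not early vs late. A test of exposure by gestational age cannot tell reverse causation from a changing drug effect. Stage II women are selected mostly before the third trimester, so interviews would seldom record why late treatment began.

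A reader might also infer that a 7-day lag should become the primary coding. The results above do not support that: it can fail to remove the bias, and it takes out nearly all treated PTD time for starts at or after 36 weeks.

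**Conclusion.** The point holds in conditional form, for the PTD Cox models of Aims 1 to 3. The plan specifies no lag and no reason-for-start rule. If reactive third-trimester starts occur, late treatment is biased towards harm and A vs B towards early treatment. At an assumed 5% share (about 30 of 10,800 women) a drug with no effect gives A vs B of roughly 0.63 to 0.79, near the .66 to .71 that Table 6 treats as detectable.

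Three stronger readings are not supported:

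- **That Aim 2 will be biased.** The documents do not show that such starts happen; without them the ratio is about 1.0.
- **That the same bias reaches LBW.** LBW uses logistic regression without time-varying exposure. When cohorts are compared as fixed groups, Cohort B must remain pregnant until treatment starts, which can push the other way: the simulated crude PTD risk ratio A/B under no effect and no reactive starts is 1.9-2.8.
- **That time-varying coding is the fault.** It is the right protection against immortal time and should stay.

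The plan should deal with this before outcomes are analysed, because a few dozen unexamined starts could produce the effect the study is looking for.

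**What to change.** Keep the time-varying coding at lag 0 as the primary PTD analysis. For PTD in Aims 1 to 3, pre-specify:

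- **(a)** sensitivity analyses at several lags, including 7 and 14 days, with each woman left in her previous exposure state during the lag;
- **(b)** an analysis using existing EMR encounter codes, in which a first treatment started on, or within a pre-specified window after, an encounter for preterm labour, ruptured membranes or planned early delivery leaves the woman in her previous exposure state;
- **(c)** the distribution of time from first dispensing to delivery among preterm births in Cohort B.

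Conclude that early treatment is better than late for PTD only if the result holds in (a) and (b). Say in advance what holding means. Similar direction and size is a workable criterion, since the lagged analyses will have too few events for significance to be informative.

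The cost is analysis wording and recoding of data the study expects to hold. Lagged analyses keep few Cohort B PTD events, because starts at or after 36 weeks add almost no lagged time before 37 weeks. Analysis (b) depends on how completely the encounters are recorded. For these reasons no lag should replace the primary coding.

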As stated above, our proposed study will provide answers to important questions that are significant challenges faced by both pregnant women and their clinicians. When making treatment decision during pregnancy, pregnant women and their physicians face the complexity of needing to consider “Treating for Two”. The results of our study will provide important evidence to allow pregnant women and their physicians to make informed decisions based on the findings of (1) the risk of PTD and LBW if not treating genital herpes infection during pregnancy; (2) the benefit of treating the infection in reducing the risk of PTD and LBW; (3) the best timing of receiving the treatment (e.g., before the 3rd trimester). Answers to those questions will be valuable to pregnant women and clinicians, and directly address their concerns when making treatment decisions.

B.4. Implications for reducing racial disparities in adverse pregnancy outcomes

It has long been recognized that racial disparities exist in parallel for both genital herpes infection and PTD: pregnant African-American women have almost **four times** of the prevalence of genital herpes (42% vs. 11% in Whites) and a **60%** higher PTD rate (17.1% vs. 10.8%)⁴³. Thus, treating genital herpes in pregnancy could reduce the racial disparity in PTD rates, which has been very difficult to achieve due to a lack of clear understanding of the factors contributing to the racial disparity. Racial disparity in PTD may be partially explained by the difference in genital herpes infection rates.

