4.5 Sample Size and Statistical Power

Given the lack of established methods for power calculations for the SMLE in our two-stage sampling scheme, we provided minimum detectable effect estimates using the results from a simulation study that we have conducted. The study provides information on the expected efficiency gains of the two-stage SMLE, relative to a standard regression analysis of the Stage II sub-sample only (with complete data on all confounders in addition to exposure and PTD/LBW status). For the purposes of our simulation study, we made a few simplifying assumptions. We assumed three exposure categories: no infection, infection with treatment, infection without treatment, with population prevalence set at 87%, 8% and 5% (similar to preliminary data), and outcome relative risks of 1.0 (ref), 1.5 and 2.0, respectively. We assumed one binary confounder measured in the Stage II sub-sample with varying prevalence across exposure categories and strength of association with outcome. The pregnancy outcome incidence was assumed at 8% (among those unexposed to infection). The Stage I sample size was 90,000, with random selection of 300 in each of the two infection/treatment categories. Relative efficiencies [i.e. $\text{Var}(\text{Stage II MLE}) / \text{Var}(\text{SMLE})$] ranged from 4 to 82 across the scenarios, demonstrating substantial gains by utilizing exposure and outcome information in the full sample of 90,000.

As an approximation to the impact of utilizing exposure and outcome information on 90,000 Stage I women in combination with the Stage II sub-sample of 1200 women, we took an “effective sample size” approach, and assumed the worst case among the simulation scenarios considered, where the relative efficiency of the SMLE was approximately 4.0. Thus, rather than basing power calculations on the Stage II sample size of 600 (300 in each group, for a two-group contrast), we based them on 2400 (i.e. $4.0 * 300$; 1,200 in each cohort category). We acknowledge that estimated gains in efficiency are based on results from a simulation study and may vary in actual analysis.

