Power calculations are based on the likelihood ratio test in the context of a Cox proportional hazards regression analysis for PTD, and a logistic regression analysis for LBW, as presented by Self⁵⁸ and as implemented in the software package EGRET⁵⁹. Given previous experience⁶⁰⁻⁶³, we expect negligible loss to follow-up (< 0.20%), a rate of PTD ranging from 8% - 12%⁶⁴, and LBW ranging from 8% to 10%⁶⁵. Each primary contrast of interest in analyses addressing **Aims 1, 2 and 5** can be characterized as a comparison of two groups of women with respect to risk of PTD and LBW. Minimum (maximum, for protective effects) detectable associations are of modest to moderate strength (Table 6). The proposed study will have more than sufficient power to detect the associations observed in our preliminary studies. Relevant to **Aim 3**, we present the maximum (protective effects assumed) detectable pattern of hazard ratios (HR) across cumulative treatment duration categories (no treatment, 1 – 10 days (45% among treated), > 10 days (55% among treated)). For the purpose of detectable effect calculations, we assume a graded, linear trend in (log) hazard/odds ratios across duration categories, a two-sided test for trend and a significance level of .05. We have sufficient power (.80) to detect a pattern of PTD HRs of 1.0 (ref), .82, and .67 associated with no treatment, 1-10 days and >10 days, respectively, assuming the worst case

scenario of expected 8% PTD rate. Similarly, we have sufficient power (.80) to detect a pattern of

Table 6. Minimum (maximum for protective scenarios) detectable hazard ratios (HR) for preterm delivery and detectable odds ratios (OR) for low birthweight in pair-wise comparisons of genital herpes exposure/treatment categories; two-sided test, significance level (α) = .05, power (1- β) =.80.

Contrast	Preterm Delivery (HR)		Low Birthweight (OR)	
	Rate = 8%	Rate = 11%	Rate = 8%	Rate = 10%
Treated infection vs. untreated infection (Aim 1; A+ B vs. C)	.71	.75	.70	.72
Treated < 3 rd trimester vs. 3 rd trimester (Aim 2, A vs. B)	.66	.71	.65	.68
Untreated infection vs. no infection (Aim 5, C vs. D)	1.51	1.40	1.54	1.47

odds ratios ORs of 1.0 (ref), .81, and .66 associated with no treatment, 1-10 days and >10 days, respectively, assuming the worst case scenario of expected 8% LBW rate.

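### Aim 2's Wald test compares preterm-delivery hazards after early and after late initiation, so births before a late start stay outside the timing contrast and a null result would not mean that timing is unimportant

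*Combined protocol and SAP*

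**What the plan says.** Section 4.2, Aim 2, fits a Cox model for PTD and specifies the exposure as follows: "Treatment will be handled as a time-varying covariate for proper classification of exposure status in each risk set for the Cox regression". The levels are "three levels: no treatment, first treatment < 3rd trimester, treatment in 3rd trimester". The early-versus-late test is then: "Significance of the difference between strength of association across the two treatment timing categories will be assessed via a Wald test".

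The background section (B.3) says what the answer is for. Patients and clinicians are to learn "the best timing of receiving the treatment (e.g., before the 3rd trimester").

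Section 3.3.3 expects 2,100 women in Cohort A (early), 2,100 in Cohort B (3rd trimester) and 6,600 in Cohort C (untreated), and allows cohort assignment to be revised at the end of pregnancy. On when late treatment starts, the nearest statement is in A.3: "Acyclovir is also recommended for treating genital herpes after 36 weeks of gestation", given there for preventing transmission to the newborn.

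Table 6 in section 4.5 has a row "Treated < 3 rd trimester vs. 3 rd trimester (Aim 2, A vs. B") with detectable HRs for PTD of .66 at an 8% rate and .71 at 11% ("two-sided test, significance level (α) = .05, power (1- β) =.80"). The effective sample size is "1,200 in each cohort category".

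**The concern.** The two coefficients being compared cover different stretches of pregnancy. The early coefficient describes the hazard from an early start onwards. The late coefficient describes only the weeks after a 3rd-trimester start. The weeks of waiting, and any preterm births in them, belong to the reference level. A woman who delivers preterm before her late treatment never reaches the late level, and on end-of-pregnancy status she would be in Cohort C.

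The Wald test therefore asks whether the hazard after starting differs by when treatment was started. A patient choosing when to start also needs to know how many preterm births happen during the wait. No section plans a comparison of PTD risk under the two start strategies. The propensity score analysis in 4.3 reuses the same exposure metrics. The exposure-by-time check described under Aim 1 does not help, because the gap exists even when hazards are exactly proportional.

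At stake are the reading of a null Aim 2 result and the Aim 2 PTD row of Table 6, which credits Cohort B with events that the model assigns elsewhere.

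**Working it through.** **1. Reproducing Table 6, Aim 2, PTD.** Inputs from 4.5: 1,200 per cohort, two-sided 0.05, power 0.80, and the PTD rate read as the overall rate in both groups. Detectable HR = exp(−2.80 × √(1/eA + 1/eB)), where eA and eB are the PTDs in each cohort.

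- 8%: eA = eB = 1,200 × 0.08 = 96; exp(−2.80 × 0.1443) = 0.67 (stated .66; Freedman's formula gives 0.664).
- 11%: eA = eB = 132; exp(−2.80 × 0.1231) = 0.71 (stated .71).

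The row reproduces when each cohort is credited with PTDs over the whole of follow-up.

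**2. Removing Cohort B's events before treatment.** The documents do not say what share this is, so it is varied.

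| Share of B's events before treatment | 8%: eA, eB | Detectable HR | 11%: eA, eB | Detectable HR |
|---|---|---|---|---|
| 0% | 96, 96 | 0.67 | 132, 132 | 0.71 |
| 25% | 96, 72 | 0.65 | 132, 99 | 0.69 |
| 50% | 96, 48 | 0.61 | 132, 66 | 0.66 |
| 75% | 96, 24 | 0.53 | 132, 33 | 0.58 |

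**3. What the test sees and what a start strategy delivers.** Let p be the untreated PTD risk, H = −ln(1 − p), h the HR after initiation (the same for both timings), and f the share of untreated PTD hazard that falls before late start. Early treatment is taken as in effect from the common starting age.

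- Early risk = 1 − exp(−hH)
- Late risk = 1 − exp(−[f + h(1 − f)]H)
- The HR ratio tested by the Wald test is h/h = 1.00.

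*Setting 1:* h = 0.66 and p = 8%, both assumed. H = 0.0834; early risk 5.35%.

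*Setting 2:* h = 0.49, the treated-versus-untreated OR in A.3 used as an HR (an assumption). p = 16%, from 4.5's 8% without infection times its relative risk of 2.0 for untreated infection. H = 0.1744; early risk 8.19%.

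| f | Setting 1: late risk | Early/late risk ratio | Setting 2: late risk | Early/late risk ratio |
|---|---|---|---|---|
| 25% | 6.02% | 0.89 | 10.21% | 0.80 |
| 50% | 6.69% | 0.80 | 12.18% | 0.67 |
| 75% | 7.35% | 0.73 | 14.11% | 0.58 |

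Steps 2 and 3 are separate illustrations. Step 2 keeps Table 6's event counts; step 3 derives risks from its own inputs.

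**4. Simulating the planned model.** This used 2,100 early, 2,100 late and 6,600 untreated women, daily risk sets from 20 weeks to before 37 weeks, three-level time-varying treatment, HR 0.49 after initiation for both timings and 16% untreated risk. Assumptions outside the documents: a PTD hazard rising 25% per week, a 3rd trimester beginning at 28 weeks, early starts spread over 20–28 weeks, an immediate constant effect, and no confounding.

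- Late starts spread over 28–36 weeks: risk 8.5% early, 11.0% late (ratio 0.77). About 126 of the 2,100 women deliver preterm while waiting. The Wald test rejects in 4.4% of replicates.
- All late starts at 36 weeks: 8.5% against 14.4% (ratio 0.59), about 271 waiting births, rejection in 5.5%.
- All late starts at 28 weeks: 8.5% against 9.1% (ratio 0.94), so the gap is small.

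For the first two patterns, with hazard shapes from flat to +45% per week, the risk ratio ran from 0.59 to 0.83 and rejection from 3.9% to 5.5%, which is the nominal level.

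**5. Unequal effects after initiation.** With a true early/late HR ratio of .66 at full Stage I size, simulated power was 0.75–0.98 for late starts over 28–36 weeks and 0.30–0.80 for starts at 36 weeks. With a stronger late effect (HR 0.35 against 0.49, late starts over 28–36 weeks), the estimated early/late ratio was 1.39, favouring late, while the strategy risks still favoured early (8.5% against 9.7%).

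**The case against.** Aim 2 asks whether timing changes the effectiveness of treatment, and comparing the two coefficients is a direct reading of that. The model also reports an estimate for each timing level. Two equal protective HRs with a null Wald test would tell a careful reader that treatment works whenever begun, and so protects for longer if begun earlier. This stands as far as it goes: the planned test is valid for its own question. It does not supply the risk comparison that B.3 promises.

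Three stronger readings are tempting, and the documents do not support them.

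- *A reader might infer that births during the wait are discarded.* They are not. They count in the untreated level and inform the early-versus-none coefficient. They are absent only from the early-versus-late contrast. Nor is that contrast an on-treatment one: the early level is defined by first treatment, and nothing says that a woman leaves a level when a course ends.
- *A reader might infer that late treatment leaves only about a week at risk.* The after-36-weeks statement concerns transmission to the newborn, and Cohort B takes any 3rd-trimester start. If every PTD preceded late start, the late coefficient could not be estimated at all, so that extreme is not a usable case.
- *A reader might infer that Aim 2's power fails.* The loss depends on late-start timing, which is not documented. At a 12% rate with half of B's events removed (144 against 72), the detectable HR is still about 0.67.

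The time-varying coding should also be defended. It avoids immortal-time bias. In the simulation, comparing observed Cohorts A and B as fixed groups gave a lower crude PTD risk in B (0.5%–7.9%) than in A (6.4%–8.2%), although late start was the worse strategy.

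**Conclusion.** The concern holds in limited form. The only planned early-versus-late PTD test is a post-initiation comparison. When effects after initiation are similar, it is null while the early/late risk ratio may lie anywhere from about 0.89 to 0.58 over the ranges in step 3, and nearer 1 if late treatment begins at the very start of the 3rd trimester. A null result would then be open to misreading as showing that timing is unimportant. If late treatment is weaker after initiation, the test can detect timing, so a false null is conditional and not inevitable.

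Table 6's Aim 2 PTD entries are optimistic to a degree that the documents do not allow to be fixed. At 8%, the detectable HR runs from 0.67 down to 0.53 over the shares examined.

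These sizes rest on the assumed share of PTDs before late start, a constant and immediate effect, an OR used as an HR in the second setting, and no confounding. The point concerns PTD. The LBW analysis uses logistic regression without time-varying coding and was not quantified here.

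**What to change.** 1. Keep the time-varying Cox model and label its Wald test in section 4.2 a comparison of hazards after initiation.
2. Add, and report beside it as the answer to the best-timing question, cumulative PTD risk by 37 weeks under two strategies from a common gestational age: start before the 3rd trimester, and start during it. Count PTDs before a late start under the late strategy. Clone-censor-weight or the g-formula with Stage I covariates will do this.
3. Do not substitute a landmark comparison against women not yet treated at the start of the 3rd trimester. On 3.3.3's numbers that group is about 6,600 / (6,600 + 2,100) = 76% never treated, so it would largely repeat Aim 1.
4. Restate the Aim 2 PTD entries of Table 6 from the PTDs expected after late initiation in Cohort B, as a range over late-start timing.

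The cost is protocol wording and extra programming on data already held, plus a less favourable stated detectable HR.
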